8.1.2 Analysis Of Survival Data

OS, PFS and treatment duration will be analyzed using Kaplan-Meier plots. Median, 25% and 75% survival times with confidence intervals for OS and PFS will be presented. For stratification according to physician's prognosis and for risk groups according to Motzer score/MIPI/Fletcher risk table, log-rank tests will be performed.

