2.2-2	Kaplan-Meier estimates for Overall survival by patient risk groups	MCL	EAS	.1 Risk groups according to MIPI score at time of primary diagnosis .2 Risk groups according to current MIPI score .3 2 nd and 3 rd line .4 2 nd to 4 th line .5 4 th line and beyond .6 5 th line and beyond .7 Patients with OR (CR+PR) .8 Patients with (MR + SD) .9 Patients with clinical benefit (CR+PR+MR+SD) .10 Patients ≤ 65 vs. patients > 65 yrs. including Kaplan-Meier curves .1 OS all patients excluding "not assessable" patients .2 OS patients with OR (CR+PR) vs. (MR+SD) vs. PD .3 OS patients with clinical benefit (CR+PR+MR+SD) vs. PD .4 OS Temsirolimus 2 nd to 4 th line (1 − 3 prior therapies) vs. 5 th line and beyond (≥ 4 prior therapies) .5 OS 2 nd to 3 rd line Temsirolimus (1 − 2 prior therapies) vs. 4 th line and beyond (≥ 3 prior therapies)
2.2-2	Kaplan-Meier estimates for Overall survival by patient risk groups	GIST	EAS	.1 Risk groups according to Fletchers risk table .2 Risk groups according to physician's prognosis
2.2-3	Frequency table of patients status by time window (survival phase)	All	EAS	
2.3	Progression free survival			
2.3-1	Kaplan-Meier estimates for Progression free survival	All	EAS Sequence analysis	Time to 25%, median and 75% survival with confidence intervals including Kaplan-Meier curve on all patients

Table No.	Title	Treatment/ Indication	Analysis set	Description
2.3-2	Kaplan-Meier estimates for Progression free survival by patient risk groups	mRCC	EAS	.1 Physicians prognosis of patients risk .2 Risk groups according to Motzer score .3 Risk groups according to modified Motzer score .4 Risk groups according to Motzer score for pretreated patients .5 by treatment sequence .6 1st line patients .7 1st line patients by risk (poor vs. non-poor) .8 2nd line vs. higher lines .9 2nd vs. 3rd line vs. higher lines .10 patients ≤ 65 yrs vs. > 65 yrs .11 by LDH low (≤ 300 U/l) vs high (> 300 U/l) .12 by histology (clear cell vs. other) Kaplan-Meier curves incl Log-Rank-Test .1 PFS 1st line vs. 2nd line and higher .2 PFS 1st line vs. 2nd line vs. 3rd line and higher .3 PFS ≤ 65 yrs vs. > 65 yrs .4 PFS LDH low (≤ 300 U/l) vs high (> 300 U/l) .5 PFS clear cell histology vs. other histology

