Description Table No. Title Treatment/ **Analysis set** Indication .1 Risk groups according to MIPI score at time of 2.3-2 Kaplan-Meier estimates for Progression free MCL EAS survival by patient risk groups primary diagnosis .2 Risk groups according to current MIPI score .3 2nd and 3rd line .4 2nd to 4th line .5 4th line and beyond .6 5th line and beyond .7 Patients with OR (CR+PR) .8 Patients with MR + SD .9 Patients with clinical benefit (CR+PR+MR+SD) Kaplan-Meier curves incl. Log-Rank-Test .1 PFS all patients excluding "not assessable" patients .2 PFS patients with OR (CR+PR) vs. (MR+SD) .3 PFS patients with clinical benefit (CR+PR+MR+SD) .4 PFS Temsirolimus 2^{nd} to 4^{th} line (1-3) prior therapies) vs. 5^{th} line and beyond (≥ 4 prior therapies) .5 PFS 2^{nd} to 3^{rd} line Temsirolimus (1 – 2 prior therapies) vs. 4th line and beyond (≥ 3 prior therapies) .1 Risk groups according to Fletchers risk table Kaplan-Meier estimates for Progression free EAS 2.3-2 **GIST** survival by patient risk groups .2 Risk groups according to physician's prognosis Physician's global assessment 2.4 Frequency table by time windows and for the last 2.4 Physician's global assessment of effectiveness mRCC **EAS** documented visit: total and by physician's prognosis of patients risk and by risk groups according to Motzer score, modified Motzer score and Motzer score for pretreated patients. Frequency table by time windows and for the last 2.4 Physician's global assessment of effectiveness MCL EAS documented visit: total and by risk groups according to MIPI score at time of primary diagnosis and

PFIZER CONFIDENTIAL

according to current MIPI score.

Table No.	Title	Treatment/ Indication	Analysis set	Description
2.4	Physician's global assessment of effectiveness	GIST	EAS	Frequency table by time windows and for the last documented visit: total and by physician's prognosis of patients risk and by risk groups according to Fletchers risk table.
2.5	Course of Karnofsky performance status scale			
2.5	Course of Karnofsky performance status scale	mRCC, GIST	EAS Sequence analysis for mRCC	Sample statistics by time windows and for the last documented visit, including absolute and relative differences to baseline (in total and by patient risk groups)
2.5	Course of ECOG performance status and B-symptoms			

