In case an event (either death or progression) was present and date of event was documented, the following definitions was used:

Overall Survival (OS, months) = $\frac{\text{date of death} - \text{date of baseline visit} +1}{365.25 *12}$

Progression Free Survival (PFS, months) = (minimum of (date of death, date of progression) – date of baseline visit + 1)/365.25 * 12.

In case information on dates were partly or completely missing or contradictory, the following was done:

• PFS:

- o the presence of a progression was confirmed, but no date was documented: if date of last intake of study medication was given, this date was used as date of progression, otherwise the date of the last visit with a documented "non-progression (e.g. SD)" was used as date of progression.
- o the presence of a progression was confirmed, but dates within a visit and on final documentation were contradictory, the prior date was used.
- o in case a death was documented within a survival follow-up/ within sequence 2 for subjects from sequence 1, but no progression was documented within regular study, the date of last visit + 1 day was used as date of progression.
- o in case no progression was documented, subject was censored with the latest available contact date / assessment date within study/within sequence.
- o in case these rules led to a missing duration or a negative duration, duration was set to "1 day".

• OS:

- o in case a death was documented, but date of death was unknown, the date of death was substituted with the latest available date for the patient (last visit, last contact date, date of assessment)
- o in case no death was documented, subject was censored with the latest available contact date / assessment date within study.
- o in case these rules led to a missing duration or a negative duration, duration was set to maximum of (PFS,"1 day").

Response to therapy (Recist criteria/ Cheson criteria)

Response to therapy according to the Recist/ Cheson criteria will be analyzed using the physician's assessment as documented in the CRF. As neither "size of lesion", "new lesions" or "increase in size" are defined as key fields, contradictory answers will not overvote physicians assessment.

"Best response" will be analyzed using the physician's assessment at final visit. If "Best response" is missing it will be determined from the best response documented during previous follow-up visits.

Treatment

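### In MCL, OS and PFS are timed from baseline but compared by best response reached later; the explicit PFS log-rank test of OR vs MR+SD favours responders by construction

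*SAP*

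**What the plan says.** **Clock.** SAP Appendix 1 (A1.3, Survival) counts both endpoints from the baseline visit; the PFS formula ends "date of progression) – date of baseline visit + 1)/365.25 * 12".

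**Grouping.** The same appendix takes best response from the physician's assessment at the final visit or, if that is missing, from the best value at earlier follow-up visits. A1.1 says visits are only suggested, every 8 to 12 weeks.

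**OS in MCL (section 9, Table 2.2-2).** The curve list has "OS patients with OR (CR+PR) vs. (MR+SD) vs. PD" and clinical benefit against PD. It opens with a curve labelled "OS all patients excluding" the not-assessable patients. The row says "including Kaplan-Meier curves" and names no test.

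**PFS in MCL (Table 2.3-2).** The row says "Kaplan-Meier curves incl. Log-Rank-Test" and lists "PFS patients with OR (CR+PR) vs. (MR+SD"). PD does not appear as a comparator in the text as extracted. A curve without not-assessable patients is listed here too.

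**Scope of the log-rank test.** Section 8.1.2 reads "For stratification according to physician's prognosis and for risk groups according to Motzer score/MIPI/Fletcher risk table, log-rank tests will be performed". The summary table in 8.2.3 lists a log-rank test for OS generally, with response to prior therapy, but not to the current therapy, among the strata. It lists none for PFS.

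**Analysis set.** Under SAP 5.1 a date of death alone admits a patient to the effectiveness set, so patients who die before any response assessment are in it.

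Neither document mentions a landmark, a time-dependent covariate or a caveat for these comparisons.

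**The concern.** Response is an outcome, but these tables use it as if it were a baseline risk group; their title refers to patient risk groups. A patient must remain under observation and progression-free until a visit before response can be recorded there, and each further visit gives another chance of being upgraded. Time from baseline to first response is therefore event-free by definition for the responder group, and the curves separate even if response has no bearing on outcome.

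Effectiveness is a stated objective, and the protocol's publication plan foresees conference abstracts and a journal paper. A small p-value for PFS by response could be read there as evidence that responding delays progression, when the calculation would give much the same result with no such link.

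**Working it through.** The documents give no MCL sample size, alpha, event count or response rate for these comparisons, so there is no planned figure to reproduce. The check asks how often the comparison rejects when response has no effect.

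**Inputs from the SAP:** time from baseline, best response over all visits, visits every 8–12 weeks (A1.1, A1.3).

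**Assumptions:** n = 50, 100 or 200; independent exponential times to death and progression with medians 8/4, 12/5 or 24/8 months; response drawn at each visit reached alive and progression-free, with probability 12% (check: 30% at the first visit only); censoring uniform over 12–60 months; two-sided 5%.

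**By hand, medians 12/5.** Fix visits at 10 weeks, d = 2.30 months, and ignore censoring.
- Event rate h = 0.693 × (1/12 + 1/5) = 0.196 per month, so mean PFS is 1/h = 5.09 months.
- Chance of passing one interval event-free: q = exp(−0.196 × 2.30) = 0.637.
- Passing a visit event-free and without response: r = 0.88 × 0.637 = 0.560. Among responders, the mean first-response visit is 1/(1 − r) = 2.27, i.e. 2.27 × 2.30 = 5.2 months of guaranteed time.
- Mean PFS for OR: 5.2 + 5.09 = 10.3 months.
- MR+SD patients also pass on average 2.27 visits, but their event falls in the next interval, after a mean of 5.09 − 2.30 × 0.637/0.363 = 1.06 months. Mean PFS: 5.2 + 1.06 = 6.3 months.

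The groups differ by about 4 months with no response effect. If response can occur only at the first visit, both groups have mean PFS 2.30 + 5.09 = 7.4 months. The bias in this comparison therefore comes from late responses, not from early deaths falling into PD.

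**Simulation, 1,000 cohorts per setting** (range over the assumed medians):

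| Comparison, no response effect | n=50 | n=100 | n=200 |
|---|---|---|---|
| PFS, OR vs MR+SD, response at any visit | 29–69% | 50–93% | 82–100% |
| OS, three groups, early deaths as PD | 24–29% | 42–58% | 68–88% |
| OS, three groups, early deaths dropped | 8–9% | 9–16% | 13–26% |
| OS, clinical benefit vs PD, early deaths as PD | 27–40% | 42–68% | 65–91% |

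With response possible only at the first visit, PFS OR vs MR+SD rejects in 5–8%. OS for clinical benefit vs PD rejects in about 4–7% when early deaths are dropped, because both groups then had to reach the first visit. A separate simulation assuming median PFS 5 and OS 12 months gave 42% (n=50) and 74% (n=100) for PFS OR vs MR+SD.

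**Size of the early-death group.** The share dying before a first visit at 2.30 months is 1 − 2^(−2.30/median OS): 18% at 8 months, 12% at 12 and 6% at 24.

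**Curves without not-assessable patients.** If these patients were exactly the deaths before that visit and survival were exponential, the median would rise by 2.3 months, for example from 12 to 14.3.

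**After a week-15 landmark:** 4.2–6.6% for PFS (OR vs not OR) and 4.7–6.4% for OS in three groups at n=200; about 5–11% at n=50–100, where groups are small.

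**The case against.** Four points have force.

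- **OS test.** A reader might infer that OS is also to be tested by response. The documents do not support that firmly. The mRCC OS row and the MCL PFS row name the log-rank test; the MCL OS row does not, and 8.1.2 does not reach response groups. The general OS entry in 8.2.3 at most implies one.
- **OS inflation.** A reader might also infer that such OS tests must reject too often. Large inflation requires early deaths to be counted as PD. The SAP has a not-assessable category for MCL best response, and if early deaths go there, clinical benefit vs PD is close to nominal and the three-group excess is much smaller. The SAP does not say which applies.
- **Not-assessable patients.** It would be wrong to say they are removed from the survival analysis generally. Tables 2.2-1 and 2.3-1 keep all patients, the restricted curves are labelled as such, and not-assessable is nowhere defined as early death. An upward shift is plausible, but its size is not established.
- **Descriptive status.** The protocol calls the evaluation purely descriptive, and SAP section 4 sets no hypothesis or decision rule. No confirmatory conclusion fails here.

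The last point lowers the severity but does not remove the defect: a p-value is still printed for PFS, and a curve with built-in guaranteed time misleads without one.

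**Conclusion.** The point stands in limited form. Grouping MCL patients by best response while timing from baseline gives responders guaranteed time. For PFS OR vs MR+SD, the response comparison with an explicit log-rank test, false rejection is about 29–69% at n=50 and 50–93% at n=100 when response can be reached at any visit, and 5–8% if only at the first. These figures rest on the assumed MCL numbers, medians, response rate and independent exponential times; the direction follows from the SAP's own definitions once responses can come after the first visit.

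For OS, a test by response is at most implied. Its inflation runs from near nominal to large (clinical benefit vs PD at n=50: about 4–7% with early deaths dropped, 27–40% with them as PD), depending on a rule the SAP leaves open. Severity: should fix. These are descriptive sub-tables for one indication, and no main estimate depends on them.

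**What to change.** In SAP section 9, MCL Tables 2.2-2 and 2.3-2:

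1. Replace the response-group curves and tests with a landmark analysis at the end of Treatment Phase 1 (week 15 in A1.1). Include only patients alive (for PFS, alive and progression-free) at that point, classify by response documented up to then, and count time from the landmark. Alternatively, enter response as a time-dependent covariate in a Cox model.
2. Drop log-rank p-values for best response timed from baseline.
3. State how patients who die before their first response assessment are classified.
4. Label the curves without not-assessable patients as conditional on being assessed, and show them beside the all-patient curves of Tables 2.2-1 and 2.3-1.
5. Reconcile 8.1.2, 8.2.3 and section 9 on where log-rank tests apply.

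The cost is SAP wording and reprogramming of a few MCL tables; no new data are needed. Patients with events before week 15 leave these tables but stay in the main curves. Later responders count as non-responders, which matters because visit timing is only suggested. With small groups the landmark test can still reject slightly above 5% (about 5–11% at n=50–100), so its p-values should be read as descriptive.
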